SYNOPSIS

PROTOCOLE PAPESCO-19

A) IDENTIFICATION OF THE CLINICAL TRIAL

TITLE OF THE TRIAL:	PAtients et PERsonnel de Santé des Centres de Lutte Contre le Cancer pendant la pandémie de Covid-19 : constitution d'une collection biologique adossée à une étude de cohorte, prospective, multicentrique.		
SHORT TITLE:	PAPESCO-19		
COORDINATOR:	[name] [name] Medical Oncologist		
Co-COORDINATOR:	[name] [name] Department of Cancer Biopathology		
METHODOLOGISTS:	[name] [name] and [name] [name] Biometry Department		
ESTIMATED NUMBER OF CENTERS:	4	NUMBER OF SUBJECTS:	15 000 - Patients: 12 000 - Healthcare personnel: 3 000

B) IDENTIFICATION OF THE SPONSOR

SPONSOR:	ICO Institut de Cancérologie de l'Ouest (ICO) Direction de la Recherche Clinique Cellule de Promotion
CONTACT:	Délégation à la Recherche Clinique et à l'Innovation (DRCI) [name] Contact: [name] [name] [contact] Email: [contact]

C) RATIONALE

Covid-19 pandemic

Coronavirus disease 2019, or Covid-19 (an English acronym meaning coronavirus disease 2019), is an emerging infectious disease caused by a coronavirus strain called SARS-CoV-2. This disease appeared in November 2019 in Wuhan, in central China. The World Health Organization (WHO) declared the outbreak a Public Health Emergency of International Concern (PHEIC) on January 30, 2020, and a pandemic on March 11, 2020. As of April 20, 2020, 166,000 deaths were estimated to be linked to Covid-19, of which around 80% occurred in Europe and the USA.

Among the main consequences, strict national lockdown measures were implemented — first in China in January 2020, then in many other countries in March (Italy, Spain, France, Switzerland, Belgium, Canada, etc.). These measures led to mass cancellations of public events, border closures, a sudden slowdown in the global economy, and unprecedented individual and social adjustments.

Early descriptive studies

The first descriptive studies of the disease originated from China and will likely need to be revised in light of the European and American data. The incubation period is estimated at 5 days (range: 2–12 days). When symptoms occur, they develop progressively: headache, muscle pain, fatigue, followed by fever and respiratory signs 2–3 days after initial symptoms.

In a number of cases, the situation continues to worsen, with chest pain, respiratory discomfort, and a radiological pattern of viral pneumonia. Signs related to involvement of other organs have been described (neurological, dermatological, etc.).

This clinical picture may be severe enough to justify hospitalization in nearly 20% of symptomatic patients and admission to intensive care in 5% of these cases. These severe forms predominantly affect certain high-risk groups, particularly older and more fragile individuals, who represent the main cause of Covid-19-related deaths.

Clinical presentation and challenges

Initial descriptive studies came from China, but European and American data suggest differences. Incubation lasts about 5 days (range 2–12). Symptoms, when present, develop progressively: headache, muscle pain, fatigue, then fever and respiratory signs 2–3 days later. Some cases worsen with chest pain, dyspnea, and viral pneumonia. Multisystemic manifestations have been reported. Around 20% of symptomatic cases require hospitalization; 5% require ICU admission—mainly affecting elderly and fragile patients.

The main diagnostic test aims to detect viral RNA in nasal secretions or sputum, quantified by RT-PCR. This PCR test, which is rather uncomfortable, appears to have a substantial false-negative rate (~30%).

Screening for minimally symptomatic or asymptomatic forms — which are likely no less contagious — is essential to slow the pandemic and prevent overwhelming the healthcare system. At present, no systematic screening strategy has been implemented in France.

Numerous serological tests detecting IgG and IgM antibodies are emerging. They are much simpler and faster than RT-PCR.

While antibody production (IgM and/or IgG) is known to be detectable from the second week after symptom onset in the general population, recent studies report the appearance of IgM and IgG antibodies as early as the 4th day after onset of clinical signs.

However, the kinetics of IgM/IgG antibody production are poorly characterized in asymptomatic or mildly symptomatic individuals, and even less so in patients with pre-existing conditions (cancer or other causes of immunosuppression).

Finally, high IgG and IgM antibody titers appear to be independently associated with disease severity.

Covid and cancer

Patients with cancer may be more susceptible to viral infections and especially more vulnerable to such infections. According to the French High Council for Public Health (HCSP), it is estimated that, for patients with cancer, the risk of hospitalization is multiplied by 4 and the risk of death by 10 compared with the general population. This excess risk is particularly pronounced in individuals presenting with lymphopenia or neutropenia — conditions frequently observed in patients receiving chemotherapy or those who have undergone multiple lines of treatment.

A higher rate of Covid-19 infection among cancer patients than in the general population may be explained by pre-existing respiratory comorbidities (e.g., lung cancer), greater medical surveillance, but also by immune fragility related to cancer treatments and shared risk factors for both cancer development and Covid-19 complications (particularly age).

However, diagnosis in these more fragile patients is currently based only on clinical symptoms (fever, cough, chest pain, dyspnea), which leads to immediate exclusion or isolation of the patient. The lack of simple diagnostic tools, the high frequency of asymptomatic forms, and the anxiety caused by this new threat have resulted in major reorganization of healthcare services: cancellations or postponements of chemotherapy sessions, imaging procedures, and surgeries. For healthcare workers, the lack of reliable testing generates anxiety and fear of contaminating patients and their families.

Impact on oncology care in France

In France, the classification of cancer patients as a “high-risk population” has led to increased vigilance and specific recommendations within oncology departments. These departments must reorganize to optimize decision-making regarding patient management schedules. Some non-urgent consultations or procedures have been postponed, and teleconsultations have been implemented. Physicians sometimes face the difficult task of weighing the consequences of delaying treatment against the risks associated with Covid-19 infection.

Strong preventive measures have been put in place. Furthermore, quarantining certain healthcare personnel can result in shortages in human resources.

Main hypothesis and objectives

Overall, patients with solid tumors, especially those recently treated with surgery or chemotherapy, appear to be at higher risk than the general population of developing severe or even fatal forms of the viral infection. However, very little data are available regarding:

- the humoral immune response to Covid-19 in cancer patients,
- the risk of respiratory complications,
- comparisons with the general population,
- differences according to systemic treatments received.

In addition, Covid-19 infections are suspected to be more severe in cancer patients due to immunosuppression, but this immunosuppression is highly heterogeneous and poorly assessed in treated or monitored cancer patients.

To date, within the network of French Comprehensive Cancer Centers (CLCC), no study has examined the extent and consequences of the Covid-19 epidemic on service reorganization. Yet this represents an important learning opportunity that could facilitate adaptation during future crises, ensuring optimal management of cancer patients.

Purpose of the study

The aim of this study is to describe the impact of Covid-19 in:

- patients undergoing treatment,
- patients who completed treatment more than one year ago,
- healthcare personnel working in CLCCs,

within a longitudinal study covering several interrelated domains ("Work Packages", WP):

- serological evolution and immune response
- clinical presentation
- epidemiology
- health economics
- psychology

Expected outcomes

We aim to:

- study the evolution of immune response in cancer patients during treatment, compare it with long-term survivors and healthcare workers
- document clinical presentations and determine whether disease course and risk factors depend on specific conditions (e.g., treatment type)
- quantify economic and organizational impacts on care, healthcare personnel, and mobilized health resources
- examine infection modes (epidemiology), despite the challenge created by interactions between the three study populations
- observe the psychological impact of this "period" on healthcare personnel by measuring their anxiety and stress levels

D) GENERAL INFORMATION ABOUT THE TRIAL

POPULATION:	Population consisting of patients and healthcare personnel from the CLCCs who fall into one of the following 3 categories during the pandemic (between March 2020 and the end of the pandemic): 
 • Patients undergoing treatment, • Patients in follow-up (having completed their treatment more than one year before inclusion), • Healthcare personnel (clinical, medical-technical, and administrative staff) of the institutions.
--------------------	--

METHODOLOGY:	
This is a prospective, multicenter cohort study with the creation of a clinico-biological database, falling within the framework of a category 2 interventional research study (RIPH 2).
 
This research will include:
 
 • The recruitment of patients receiving care in participating centers who attend within the context of their treatment or follow-up during the inclusion period, and the recruitment of healthcare personnel working within these same institutions. • A collection of blood samples (biobank). • Biological and clinical data collected from patient medical records. • Psychometric questionnaires (STAI state, STAI trait, PTGI, HADS) (ANNEXES 8 to 11) and the “Healthcare Personnel” questionnaire (ANNEXE 7) completed by staff. • Sociodemographic, lifestyle, and Covid-19 clinical-symptom questionnaires completed by both personnel and patients (ANNEXES 4 to 6). • PMSI data. • Focus groups with healthcare personnel to explore different behaviors in response to changes. 
A semiannual extraction of data may be considered for exploratory analyses.

NUMBER OF SUBJECTS:	
As this is a cohort study involving the creation of a clinico-biological database, the number of subjects directly depends on the recruitment potential of each center. Based on the information provided by the 4 participating CLCCs, the cohort size has been estimated at 15,000 subjects distributed as follows:
 
 • Number of patients (in treatment and follow-up): 12,000 • Number of healthcare personnel: 3,000
MAIN OBJECTIVE:	
Creation of a clinico-biological database to describe Covid-19 infections (incidence and severity) among CLCC patients and personnel.

SECONDARY OBJECTIVE:	
WP 1: SEROLOGY MANDATORY
 
Evaluate the humoral response to a Covid-19 infection in the following subgroups:
 
 In patients with cancer who are symptomatic with a probable Covid-19 infection In patients whose treatment has been suspended In patients with treatment currently ongoing: 
 Patients receiving immunotherapy Patients receiving chemotherapy: 
 Patients with neutropenia-inducing chemotherapy Patients with lymphopenia-inducing chemotherapy In healthcare personnel of the CLCCs 
Describe the diagnostic performance of serological tests (IgM rapid test and IgM serological test).
 
Describe long-term IgG persistence and quantification (Month 12) in populations from the CLCCs.
 
Among individuals who developed IgG:
 
 describe the frequency of reinfections in each study population. describe the protective IgG threshold in each study population. 
Evaluate the influence of polymorphisms in low-affinity Fc gamma receptors for IgG (FcγRIIa, FcγRIIIa) on the humoral response.
 
Evaluate the appearance of IgG and their evolution during study follow-up after vaccination.
 
Evaluate the number of individuals presenting antibodies after vaccination.

	
Evaluate the neutralizing capacity of IgG (neutralization assays) after vaccination over the duration of the study.
 
WP 2: CLINICAL MANDATORY
 
Describe severity (asymptomatic, symptomatic, prolonged, severe, fatal) by age group:
 
 In healthcare personnel In cancer patients In patients in follow-up In patients undergoing treatment: 
 Receiving chemotherapy and according to whether the chemotherapy induces grade 3–4 neutropenia or lymphopenia (as defined in the primary literature) Receiving immunotherapy 
Determine the frequency of Covid-19 reinfection (recurrence of clinically suggestive symptoms with positive viral PCR and/or positive IgM serology) during follow-up in the different groups.
 
Identify risk factors (clinical and therapeutic) for developing severe forms of Covid-19 infection among patients.
 
WP 3: ECONOMIC ANALYSIS OPTIONAL FOR CENTERS
 
Describe the consequences of Covid-19 in terms of organizational changes and care practices, from the start of the epidemic until the end of systematic screening for patients and healthcare personnel.
 
Identify changes in healthcare personnel practices regarding:
 
Coordination between healthcare workers
 
 Communication Patient management 
Identify resources associated with organizational changes at the level of:
 
 Modification of treatment regimens for patients (e.g., chemotherapy, radiotherapy, surgery) Organization of teleconsultations Diagnostic investigations for new cancers 
Analyze the impact of changes on patient health status.
 
Evaluate resources allocated to:
 
 The organizational changes described above Systematic screening of patients and healthcare personnel Work stoppages. 
WP 4: PUBLIC HEALTH / EPIDEMIOLOGY OPTIONAL FOR CENTERS
 
Identify risk factors for SARS-CoV-2 infection among patients, including:
 
 Sociodemographic factors (age, socio-professional category, housing, cohabitation) Lifestyle (work modalities, mobility, protective measures, etc.) Contact with infected individuals at work or at home Care pathway in CLCCs (number and duration of visits, number of care units visited, etc.), use of community care 
Estimate SARS-CoV-2 infection prevalence at the end of the lockdown:
 
 among patients among healthcare personnel who continued onsite work among healthcare personnel who were confined 
Identify risk factors for Covid-19 infection among healthcare personnel, including:
 
 Sociodemographic factors (age, socio-professional category, housing, cohabitation) Lifestyle (work modalities, mobility, protective measures, etc.)
--	---

	
c. Contact with infected individuals at work or at home d. Use of community care
 
Describe the incidence of Covid-19 infections among patients and healthcare personnel.
 
Compare the distribution of contamination risk factors among patients and those of the general population (Constances cohort).
 
Describe adherence to SARS-CoV-2 vaccination among personnel and patients.
 
WP 5 : PSYCHOLOGY OPTIONAL FOR CENTERS
 
Examine the evolution of state anxiety over time and determine whether perceptions of anxiety evolve, indicating a possible adaptation process.
 
Examine associations between post-traumatic growth, trait anxiety, sociodemographic variables, and the evolution of state anxiety over time.
 
Examine the evolution of depression over time and determine whether perceptions of depression evolve, indicating a possible adaptation process.
 
Examine associations between post-traumatic growth, trait anxiety, sociodemographic variables, and the evolution of depression over time.

INCLUSION CRITERIA:	
 1) Age \geq 18 years; 2) Population from a CLCC meeting one of the following three definitions: 
  patients undergoing treatment,  patients in follow-up (having completed their treatment more than one year prior to inclusion),  healthcare personnel; 3) Subjects having had or not had an infection compatible with, or confirmed as, Covid-19; 4) Subjects informed and having signed the informed consent form; 5) Subject affiliated with a social security system.
NON-INCLUSION CRITERIA:	
 1) Refusal to provide consent; 2) Patients unable to give consent or presenting psychiatric history; 3) Inability to comply with medical follow-up for geographical, social, or psychological reasons; 4) Individuals under legal protection (guardianship or curatorship); 5) Individuals deprived of liberty by judicial or administrative decision.
PRIMARY EVALUATION CRITERION:	
Biological data: Serological status (rapid immunochromatographic test) and IgM and IgG titers (enzyme immunoassay, ELISA type), performed at M0, M3, M6, M9, and M12. Collection via questionnaire of results from tests detecting SARS-CoV-2 viral genome (RT-PCR molecular test) performed in community settings
 
Clinical data: Follow-up questionnaire on clinical signs suggestive of Covid-19.

COMPLETION EVALUATION CRITERION:	
WP 1: SEROLOGY MANDATORY
 
Time to appearance and titers of anti-SARS-CoV-2 IgM and IgG at the different measurement timepoints in each subgroup. Specificity, sensitivity, PPV (Positive Predictive Value), and NPV (Negative Predictive Value) from the different tests, with quantitative serology (ELISA) considered the gold standard.
 
IgG levels at M12.
 
Number of reinfections or viral reactivations (appearance of clinical signs confirmed by RNA tests — RT-PCR positive — and serology) in the subgroup of patients who developed IgG.
 
Anti-SARS-CoV-2 IgG titers according to the occurrence or absence of reinfection during follow-up.

	
Time to appearance and titers of anti-SARS-CoV-2 antibodies according to FCGR2A and FCGR3A genotypes.
 
IgG-positive results on rapid TROD tests and semi-quantitative ELISA IgG titers in vaccinated individuals.
 
Number of vaccinated individuals in whom anti-Spike protein IgG titration is feasible.
 
Number of vaccinated individuals with positive neutralization test results.
 
WP 2: CLINICAL MANDATORY
 
Number of Covid-19-related deaths, severe infections (requiring oxygen therapy), prolonged symptomatic infections, moderate infections, and asymptomatic infections, relative to all subjects in the population with seropositivity and/or a positive RT-PCR test, as well as duration of the symptomatic phase.
 
Reinfection cases are defined as recurrence of clinical symptoms and/or positive viral PCR and/or positive IgM serology after a symptom-free interval. Frequency is defined as the number of reinfection cases relative to all subjects in the population with seropositivity and/or a positive RT-PCR test.
 
Among subjects in the population with seropositivity and/or a positive RT-PCR test, factors significantly associated with severe forms / mortality among the following:
 
 ○ Ongoing or recent anticancer treatment: 
 - Immunotherapy - Chemotherapy, according to frequency of grade 3/4 neutropenia and/or lymphopenia - Radiotherapy - Surgery ○ Concomitant treatments ○ Comorbidities ○ Cancer (cancer type, stage, etc.) ○ Cancer-related medical history (number of treatment lines, surgical and medical history) ○ Biological markers (CRP, etc.) 
WP 3: ECONOMIC ANALYSIS OPTIONAL FOR CENTERS
 
Type of organizational and practice changes implemented and their frequency according to specialties/services.
 
Total number of patients affected and number of patients per type of change.
 
Positive or negative effects on patient morbidity or mortality.
 
Monetary value of resources mobilized (increased or decreased) depending on observed changes.
 
Number and duration of healthcare personnel sick leave.
 
Benefits of organizational changes for healthcare personnel.
 
Costs of systematic screening of patients and healthcare personnel..
 
WP 4 : PUBLIC HEALTH / EPIDEMIOLOGY OPTIONAL FOR CENTERS
 
Number of SARS-CoV-2 infections among all monitored patients.
 
Prevalence of SARS-CoV-2 infection/immunization during the 3 weeks following the end of lockdown among patients, healthcare personnel working onsite, and healthcare personnel who were confined, by age group, by region (center), and according to comorbidities.
 
Number of SARS-CoV-2 infections among all monitored healthcare personnel.
 
Quarterly incidence rates among patients and healthcare personnel by age group, by region (center), and according to comorbidities.
 
Percentages (qualitative variables) / means or medians (quantitative variables).

--	--

	
Percentage of personnel and patients refusing vaccination, and distribution according to reasons for refusal.
 
WP 5 : PSYCHOLOGY OPTIONAL FOR CENTERS
 
a. and b. State anxiety score at 3, 6, 9, and 12 months. c. and d. Depression score at 3, 6, 9, and 12 months.
 
Variables assessed at T0 (before screening) State anxiety (STAI-State questionnaire, Spielberger, Gorsuch, Lushene, Vagg & Jacobs, 1983; 20 items) Post-traumatic growth (PTGI, Tedeschi & Calhoun, 1996; 21 items; induction instruction: "since the lockdown"). The PTGI evaluates perceived positive changes such as shifting life priorities, closer relationships with others, developing new interests, etc. Trait anxiety (STAI-Trait questionnaire, Spielberger et al., 1983; 20 items) Sociodemographic variables (related to the Epidemiology WP) Depression (HADS questionnaire, Zigmond & Snaith, 1983; 14 items)
 
At 3, 6, 9, and 12 months (within the week following screening) State anxiety (STAI-State, 20 items) Depression (HADS, 14 items)

--	---

E) DESCRIPTION OF THE STUDY INTERVENTIONS

In this study, screening of patients and healthcare personnel will be performed using two or even three techniques depending on the result:

- **Repeated blood sampling, performed at inclusion (M0), Month 3 (M3), Month 6 (M6), Month 9 (M9), Month 12 (M12), plus on demand in the event of Covid-19 symptoms:**
 - a) Rapid serological test (TDR) — qualitative
 - Performed immediately on site.
 - Technique: immunochromatography strip detecting IgM / IgG.
 - b) Serology by ELISA — quantitative
 - Performed later on frozen samples.
 - c) Genotyping of FCGR2A and FCGR3A genes
 - Performed only at M0.
- **Nasopharyngeal swab (RT-PCR)**
 Detection of viral RNA.

This examination is performed with immediate result exclusively in the event of symptoms, irrespective of the rapid test result, for patients hospitalized in a Covid unit when such a unit exists within the center.

Results of RT-PCR tests performed in community settings (outside the hospital) will be collected via questionnaires.

- **Questionnaires** (Linked to the Work Packages — some are therefore optional)
 - Patients : Q1, Q2, Q3
 - Healthcare personnel : Q1, Q2, Q3, Q4, STAI (ETAT & TRAI), PTGI, HADS

TRIAL SCHEDULE

INCLUSION PERIOD:	12 months
DURATION OF PARTICIPATION PER SUBJECT:	12 months
MINIMUM PARTICIPATION TIME PER PATIENT:	12 months
OVERALL STUDY DURATION:	24 months
START OF THE CLINICAL TRIAL:	June 2020
END OF THE CLINICAL TRIAL:	Last follow-up of the last patient included: May 2022

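### The WP 2 reinfection rules do not clearly require the second positive to be new, and the WP 1 criterion places reactivations in the same count

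*Protocol*

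**What the plan says.** Reinfection is described in four places in section D of the protocol synopsis.

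- **Secondary objective, WP 2:** "recurrence of clinically suggestive symptoms with positive viral PCR and/or positive IgM serology". Symptoms are needed together with at least one positive test.
- **Completion evaluation criterion, WP 2:** "Reinfection cases are defined as recurrence of clinical symptoms and/or positive viral PCR and/or positive IgM serology after a symptom-free interval". Read plainly, any one of the three is enough. The denominator follows: "Frequency is defined as the number of reinfection cases relative to all subjects in the population with seropositivity and/or a positive RT-PCR test".
- **Secondary objective, WP 1:** among people who developed IgG, "describe the frequency of reinfections in each study population".
- **Completion evaluation criterion, WP 1:** "Number of reinfections or viral reactivations (appearance of clinical signs confirmed by RNA tests", which goes on to require a positive RT-PCR and serology. A further WP 1 criterion compares IgG titres between people with and without reinfection.

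Section E plans serology at M0, M3, M6, M9 and M12, and on demand when symptoms occur. Study RT-PCR is limited to symptomatic patients hospitalised in a Covid unit, where the centre has one; community results come by questionnaire. The inclusion criteria admit people who have already had Covid-19.

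**The concern.** A reinfection count needs some evidence that the second positive belongs to a second infection: a minimum interval, a negative test in between, or a rise in titre. None of these is stated. The only guard is the symptom-free interval in the WP 2 criterion, which has no length and concerns symptoms rather than clearance of IgM or RNA.

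Two kinds of subject show the gap. One is IgM-positive at M0, has a cold some weeks later, and is still IgM-positive at the on-demand draw; this meets the WP 2 objective. The other has no symptoms and is still IgM-positive at the next quarterly visit; on a plain reading this meets the WP 2 criterion.

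The reported frequency would be too high. The rationale (section C) calls antibody kinetics poorly characterised in mild or asymptomatic infection, and even less well known in patients with cancer or immunosuppression. Equal clearance in treated patients, follow-up patients and staff therefore cannot be assumed, and a difference between groups could reflect clearance rather than reinfection.

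**Working it through.** The protocol gives no reinfection rate, persistence rate or expected count, so there is no figure to reproduce. The check compares the rules and then works through a range.

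**Step 1. What each rule accepts**

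- WP 2 objective: leftover IgM or RNA counts if suggestive symptoms from another cause occur while it persists.
- WP 2 criterion, plain reading: leftover IgM or RNA counts by itself once symptoms have ceased.
- WP 1 criterion: signs, RT-PCR and serology are all needed, so leftover IgM alone does not count. Residual RNA with unrelated symptoms, or a reactivation, can. The subgroup already has IgG, so the serology condition adds little unless a rise or a new response is required.

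**Step 2. Inputs (all assumptions, none from the protocol)**

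- r, true reinfection among infected subjects over follow-up: 1–3%.
- q, lingering IgM or RNA positivity found at a later test: 5–20%.
- s, suggestive symptoms from another cause at that time: 10%.

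**Step 3. Residual share of counted cases = L / (L + r)**

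Positive test alone suffices, L = q:

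- q = 5%, r = 3%: 0.05 / 0.08 = 0.63
- q = 10%, r = 3%: 0.10 / 0.13 = 0.77
- q = 10%, r = 1%: 0.10 / 0.11 = 0.91
- q = 20%, r = 1%: 0.20 / 0.21 = 0.95

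Symptoms also needed, L = q × s = 0.10 × 0.10 = 0.01:

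- r = 3%: 0.01 / 0.04 = 0.25
- r = 1%: 0.01 / 0.02 = 0.50

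Over q = 5–20% at the same s, L is 0.005 to 0.02, and the share runs from 0.005 / 0.035 = 0.14 to 0.02 / 0.03 = 0.67.

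**Step 4. Effect on a group comparison**

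Suppose r = 2% in two groups, with q = 5% in one and 20% in the other. If a test alone suffices, the counted frequencies are 2 + 5 = 7% and 2 + 20 = 22%. If symptoms are also needed (s = 10%), they are 2 + 0.5 = 2.5% and 2 + 2 = 4%. True reinfection is the same in both groups.

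**Step 5. Wider ranges**

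Take r = 0.5–5%, q = 5–40%, s = 5–30%, and detection of true cases (se) of 0.70 or 0.90. The 0.70 comes from the RT-PCR false-negative rate of about 30% given in section C. True cases are r × se; residual cases are q(1 − r) or q × s × (1 − r).

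- Test alone: residual share 0.51–0.99, above one half in all 32 combinations. At se = 0.70, true cases lead only if r exceeds q / (0.70 + q): 6.7% at q = 5%, 12.5% at q = 10%.
- Symptoms also needed: residual share 0.05–0.97, above one half in 58 of 96 combinations. Break-even at q = 10%, s = 10% is 0.01 / 0.71 = 1.4%.

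**Step 6. Would one negative RT-PCR in between be enough?**

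Take r = 1%, q = 10%, s = 10%, se = 0.70, with a 30% chance that a test during residual positivity reads negative. Per 1,000 infected subjects there are 7.0 true cases. With symptoms required, residual cases fall from 9.9 to about 3.0 (share 0.59 to 0.30). With a test alone, they fall from 99 to about 30 (share 0.93 to 0.81). One negative helps but does not solve the problem.

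**The case against.** Several objections have force.

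- **Recurrence may govern all three items.** In the WP 2 criterion the word can be read to cover PCR and IgM as well as symptoms, and unbroken IgM positivity is no recurrence. This reading is possible, which is why the point is that novelty is not clearly required. It does not help with the WP 2 objective, where only the symptoms recur, and it still leaves no test of what makes a positive recurrent.
- **One figure for both WP 2 rules.** A reader might infer that residual positivity dominates under either rule. That is not supported: the 63–95% range fits only the reading in which a test alone suffices. Nor can the rarity of reinfection be taken as fact, since the protocol gives no rate.
- **Effect on the protective-IgG work.** A reader might infer that IgM-only cases enter it. They do not, because WP 1 needs signs, RT-PCR and serology. The IgG comparison refers to reinfection and does not name reactivations, so their entry there is possible, not established.
- **Pooling.** "Number of reinfections or viral reactivations" does not forbid separate tabulation, and an analysis plan could provide it. Still, the criterion as stated is wider than its objective.
- **Weight.** These are secondary, descriptive results, and serial samples allow cases to be reclassified at analysis. That limits the severity but does not repair the stated rule.

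**Conclusion.** The point holds as a fault in a stated definition, not as missing detail. As written, the WP 2 rules allow leftover IgM or RNA to be counted as reinfection, and the WP 1 criterion goes beyond its objective by naming reactivations. The direction of the bias is upward. Its size depends on assumed rates and on which WP 2 rule is applied: residual cases are the majority throughout the assumed ranges if a positive test alone suffices, and anything from a small minority to nearly all cases if symptoms are also required. Distortion between groups follows only if clearance, or the frequency of unrelated symptoms, differs between them, which the protocol gives no data to judge. In WP 1 the risk is confined to residual RNA or reactivation. The definition should be corrected before analysis, since both work packages are mandatory; it does not threaten the main objective of building the database.

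**What to change.** Reconcile the WP 1 and WP 2 texts into one analysis definition, including whether symptoms are required, and add the following.

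- **IgM-based case:** count only if an IgM-negative study sample lies between the first episode and the new positive, or if paired ELISA titres show a rise of a size set in advance.
- **RT-PCR-based case:** count only after a fixed minimum interval since the first positive, for example one sampling interval (3 months). A single negative RT-PCR in between should not replace the interval, given the stated false-negative rate and the limited study RT-PCR testing.
- **Other cases:** report as *possible* reinfection, including those whose first episode cannot be dated because it preceded inclusion.
- **Viral reactivations:** report on a separate line, outside the reinfection count and outside the IgG comparison by reinfection status.

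The cost is a change of text; the samples and results are already planned. The price is that some early true reinfections move to *possible*. Their number is unknown and may differ by group if clearance does, so both counts, strict and strict plus possible, should be shown for each group.
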